5.4.3 Pharmacokinetic Similarity Assessment

For population included in PKSS, the primary PK parameters, C_{max} , $AUC_{0-\infty}$ are converted by natural logarithm to perform significance test using Mixed Model, with formulation factors as fixed effects. The PK similarity of proposed biosimilar (Test) products and reference products will be evaluated by statistical analysis method of calculating 90% Cis. And the 90% CIs of the Test/Reference GMRs have to fall in the range of 80% - 125% to demonstrate the PK similarity.

T_{max} will be compared with rank test and p value will be provided.

The above statistical analysis will be performed using SAS 9.4 or higher.

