11 Sampling for immunogenicity assessment: A total of four (4) blood samples for each participant will be collected for determination of serum anti-drug antibodies (ADA) / neutralizing antibodies (Nab) at 0 h (within 30 minutes pre-dose) and Day 16, Day 30, Day 65 post-dose. The actual sampling time should be recorded;

12 Participants will be discharged from the clinical research facility after PK sampling and required safety assessment at approximately 72 h after dosing while OPVs are required at approximately 96 h (Day 5), 120 h (Day 6), 144 h (Day 7), 168 h (Day 8), 216 h (Day 10), 288 h (Day 13), 360 h (Day 16), 528 h (Day 23), 696 h (Day 30), 864 h (Day 37), 1032 h (Day 44), 1200 h (Day 51), 1368 h (Day 58), 1536 h (Day 65) post-dose;

13 Safety tests will be performed at the end of trial on Day 65 for each participant before discharge from the trial, including physical examination, laboratory tests [biochemistry, hematology, urinalysis, coagulation function, serum pregnancy test (only for females)], ECG, vital signs; and also the weight of participants will be collected;

14 Any dosed participants who withdraw ahead of time should receive the scheduled safety tests for permission to discharge from the trial before leaving or at the time of the participants next scheduled follow-up visit, or any other time appropriate in discretion of investigators. In addition collection of weight will be performed.

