5.3 Inclusion Criteria

- 1) Able to provide signed Informed Consent Form before the trial, and fully understand the trial content, process and possible adverse drug reactions (ADRs);
- 2) Able to complete the trial in compliance with the protocol;
- 3) Participants (including males) willing to adopt effective contraceptive methods and with no pregnancy plan from 14 days before screening to 6 months after the last scheduled visit;
- 4) Males and females between 18 and 55 years old, inclusive;
- 5) At least 50 kg for participants, with a Body Mass Index (BMI) = Weight/Height² (kg/m²) between 19.0-26.0 kg/m², inclusive;
- 6) No history of chronic or serious cardiac, hepatic, renal, digestive tract, nervous system, hematologic, respiratory, dermatological, mental and metabolic disorders, *etc.*

Only those who meet all the criteria listed above can be enrolled.

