8 TRIAL ASSESSMENTS AND PROCEDURES

8.1 Screening/Baseline Assessments and Procedures

Healthy males and females of age 18 – 55 years old inclusive will be enrolled. After providing written informed consent, participants will undergo a complete collection of data within 28 days prior to investigational products dosing including:

- Demographic data (including gender, age, height, weight, BMI, nation, and race, *etc*).
- Medical /surgical history, allergy history, medication history, drug abuse history, history of tobacco and alcohol.
- Chest X-ray.
- Physical examination (detailed in [Section 8.3.1](#))
- Vital signs (detailed in [Section 8.3.2](#))
- ECG (detailed in [Section 8.3.3](#))
- Clinical laboratory tests [biochemistry, hematology, urinalysis, coagulation function, antinuclear antibody, viral tests (HBV, HCV, HIV, syphilis, tuberculosis) and a serum pregnancy test (females only), see [Section 13.2](#)].
- A urine drug abuse test (Morphine, Methamphetamine, Ketamine, Tetrahydrocannabinol and Methylenedioxymethamphetamine in urine) and alcohol breath test.

Viral tests results obtained within the previous 3 months prior to investigational products dosing may be used instead of obtaining these tests at the screening visit. Among them, the urine drug abuse test and alcohol breath test will be conducted before check-in (Day -1) and retested upon OPVs on Day 30.

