1.6 Sample Size Determination

Based on literature information, it is estimated that the inter-subject coefficient of variation of the primary PK parameters is approximately 44%. α is set to be 0.05; the power of detecting the PK similarity of the proposed biosimilar / reference product is 90%, the T/R GMR is assumed to be 1.05, the equivalent threshold is 0.80~1.25, taking risk of drop-out into account (approximately 15%), 238 participants are to be enrolled in the parallel trial.

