5.2 Demographic Data and Baseline Characteristics

Demographic and baseline characteristics will be summarized for all participants included into FAS.

For age, weight, height and BMI: the number of cases, arithmetic mean, standard deviation, median, quartile, min and max will be statistically summarized.

For gender, Ethnicity, race: the cases and percentage will be statistically summarized.

For medical history, surgical history: classification according to MedDRA (Version 27.0 or higher) and the cases and percentage will be statistically summarized.

For smoking/alcohol/allergy/drug abuse history, viral tests, alcohol breath tests and drug abuse tests, antinuclear antibody tests, tuberculosis diagnosis as well as chest X-ray: the cases and percentage will be statistically summarized.

5.3 Medications before Study Drug, Concomitant Medications and Concomitant Non-Drug Therapy Record

Medications before Study Drug, Concomitant Medications and Concomitant Non-Drug Therapy Record will be coded using the World Health Organization (WHO)-Drug, and listed by reported term / preferred term and Anatomical Therapeutic Class classification. Medications before Study Drug, Concomitant Medications and Concomitant Non-Drug Therapy Record taken by participant included into FAS will be listed and statistically summarized with cases and percentage.

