5.4.4 Sensitivity Analysis

Outlier: Observation extremely discordant with the average level. Outlier may be

caused by the great variability of the variables, or may be an error due to a mistake which can be treated as a missing data however the mistake should be clarified.

Sensitivity Analysis: Sensitivity analyses are a series of analyses conducted against the unexpected conditions, e.g. analysis for data with missing data filled in, subgroup analysis, analysis for a different dataset, adjustment of different covariates, etc. The sensitivity analysis result will be compared with that from the due analysis to explore the robustness of inferences. Sensitivity analysis results can be a supportive data to the main analysis, however, it cannot be the primary rational to make a conclusion.

The sensitivity analysis method is the same as the pharmacokinetic similarity method.

Sensitivity analysis on the outlier or other cases can be conducted, if warranted, during the PK similarity analysis. Influence of outliers can be evaluated by comparing the assessment results in cases with the outliers excluded or not. Reasons should be explained if different conclusions are reached.

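### Optional improvement, not an error: the primary PK model could use screening weight, already collected, as a covariate for a small and conditional gain in precision

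*SAP*

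**What the plan says.** The primary comparison is fitted to ln Cmax and ln AUC0-inf "using Mixed Model, with formulation factors as fixed effects" (SAP 5.4.3; Protocol 9.2.1.2 has the same wording). The Statistical Analysis row of the Protocol 1.1 synopsis calls it an analysis of variance. None of the three names a covariate. Similarity requires both 90% CIs to lie within 80–125%.

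Weight is available before dosing: Protocol 8.1 lists "Demographic data (including gender, age, height, weight, BMI, nation, and race" at screening, and BMI eligibility depends on it. A second weight is taken on Day 65 (Protocol 1.3, footnote 13: "and also the weight of participants will be collected"). The SAP uses weight only descriptively (SAP 5.2: "For age, weight, height and BMI: the number of cases", followed by summary statistics). Covariates otherwise appear only as an unnamed example among the sensitivity analyses, "adjustment of different covariates, etc" (SAP 5.4.4). That section says of a sensitivity result that "it cannot be the primary rational to make a conclusion".

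For planning, "it is estimated that the inter-subject coefficient of variation of the primary PK parameters is approximately 44" per cent (SAP 1.6), with GMR 1.05, limits 0.80–1.25, 90% power, about 15% dropout and 238 enrolled.

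**The concern.** Each participant is dosed once, so all between-subject variance enters the confidence interval. Everyone receives 40 mg whatever their weight. If exposure falls as weight rises, part of that variance could be explained by a baseline value the trial already holds, and the planned model leaves it in the error term. At stake is a modest loss of precision on both primary endpoints; validity is not affected.

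**Working it through.** **The plan's own figure first.** The ln-scale variance is ln(1 + 0.44²) = 0.1770, so σ = 0.4207. Then 238 × 0.85 = 202.3, or 101 evaluable per arm. Exact power for two one-sided 5% tests at GMR 1.05 with limits 0.80–1.25 is 0.8999. Working back, 202/0.85 = 237.6, rounded up to 238. The stated sample size reproduces with the unadjusted model.

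**Unadjusted interval at 101 per arm.** SE = 0.4207 × √(2/101) = 0.0592. Half-width = t(0.95; 200) × SE = 1.6525 × 0.0592 = 0.0978. At an observed GMR of 1.05 the 90% CI is 95.2–115.8%.

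**Adjusted interval.** Formulas:
- R² = (SD of ln weight × slope)² / 0.1770
- half-width = t(0.95; 2n−3) × σ√(1−R²) × √(2/n) × √(1 + 1/(2n−4)), where the last factor allows for chance imbalance in weight.

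**Assumed inputs, not in the documents.** SD of ln(weight) 0.08–0.14; absolute slope of ln exposure on ln weight 0.5–1.0, with 0.25 and 0 as checks. The slope may differ between Cmax and AUC0-inf. The entry limits (at least 50 kg, BMI 19.0–26.0; Protocol 5.3) guide the SD range. At a fixed height, BMI alone allows an ln(weight) span of ln(26/19) = 0.314, which is an SD of 0.314/√12 = 0.091 if uniform. Spread in height adds to this, and the 50 kg floor trims it.

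| SD | Slope | R² | Half-width | Change | Power |
|---|---|---|---|---|---|
| any | 0 | 0% | 0.0981 | 0.25% wider | 0.8985 |
| 0.08 | 0.25 | 0.2% | 0.0980 | 0.14% wider | 0.8991 |
| 0.14 | 0.25 | 0.7% | 0.0977 | 0.09% narrower | 0.9004 |
| 0.08 | 0.5 | 0.9% | 0.0976 | 0.2% narrower | 0.9009 |
| 0.10 | 0.5 | 1.4% | 0.0974 | 0.5% narrower | 0.9023 |
| 0.10 | 1.0 | 5.6% | 0.0953 | 2.6% narrower | 0.9134 |
| 0.14 | 1.0 | 11.1% | 0.0925 | 5.5% narrower | 0.9272 |

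Worked for the last row: R² = (0.14 × 1.0)²/0.1770 = 0.0196/0.1770 = 0.111. Half-width = 1.6525 × 0.4207 × √0.889 × √(2/101) × √(1 + 1/198) = 0.0925. At GMR 1.05 the CI becomes 95.7–115.2%.

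**Break-even.** The adjusted interval is narrower once R² exceeds about 0.5%, that is, once SD × slope exceeds 0.030. This needs a slope above 0.030/0.08 = 0.37 at the low SD, or 0.030/0.14 = 0.21 at the high SD.

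**If nobody drops out (119 per arm).** Unadjusted power is 0.938, so there is less left to gain.

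**The case against.** The strongest reply is that this is a preference between two valid models, resting on a relation the documents never state. Neither document links weight to Cmax or AUC or gives an SD or slope, and the entry limits deliberately narrow the weight range. With a weak slope the gain vanishes. All of that stands; it is why the result is a range that includes no gain.

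An SD as high as 0.16 would give R² of 14.5% and power of 0.935, but it does not fit the entry limits. If ln(weight) were uniform from 50 kg, weights would have to be spread evenly up to 50 × exp(0.16 × √12) = 87 kg, which at BMI 26 means a height of about 1.83 m. I do not rely on it.

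A second reply is that SAP 5.4.4 already permits covariate adjustment, so weight could be named there. That is less disruptive and would give a robustness check. It would not sharpen the primary interval, because that section bars sensitivity results from carrying the conclusion.

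A third is that randomisation is stratified (SAP 1.4). The factors are not named. If weight or sex is among them the arms are better balanced, but a formulation-only model still leaves the weight variance in the residual. What does stand is that stratum terms, if added, might absorb some of the same variance. The extra gain from weight beyond such terms cannot be judged from the documents.

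A reader might infer that the planned analysis is biased or underpowered, or that 238 is too few. The documents do not support this. Randomisation protects the comparison, the unadjusted CI already allows for chance imbalance in weight, and 238 delivers the stated power without adjustment.

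**Conclusion.** The point holds as a low-priority, optional improvement. The planned model is valid. If the assumed SD and slope are right, ln(weight) explains about 1–11% of the ln variance, and power per endpoint rises by about 0.1 to 2.7 percentage points. If weight is irrelevant, the loss is about 0.1 point. The effect on the decision is small either way: at an observed GMR of 1.05 the interval is well inside 80–125% with or without the covariate. The size of the gain rests entirely on the assumed SD and slope, so a sponsor could reasonably decline.

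**What to change.** While treatment assignment is blinded and before database lock:

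- Name ln(screening weight) as a covariate in the single declared primary model for both endpoints, in SAP 5.4.3 and Protocol 9.2.1.2. Specify the screening value; the Day 65 weight is measured after dosing.
- Keep the formulation-only model as a named sensitivity analysis.
- Conform the Protocol 1.1 synopsis, which describes an analysis of variance without covariates.
- Conform SAP 5.4.4, which says sensitivity analyses use the same method as the similarity analysis. A formulation-only sensitivity analysis would contradict that.

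The cost is one degree of freedom, no new data, and edits in at least four places. The documents' own approval steps also apply. A revised SAP must record its reasons and repeat the original review and approval (Protocol 9). A protocol amendment needs the principal investigator, the sponsor and then the ethics committee (Protocol 13.4; Protocol 10.2 speaks of approval by or filing to the committee).

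The documents require the SAP to be final before data lock (SAP 1) and assignment to stay blinded until the database is locked (SAP 1.5), but do not show whether that window is still open. If it has closed, leave the planned primary model unchanged.

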5.4.4 Sensitivity Analysis

Outlier: Observation extremely discordant with the average level. Outlier may be

caused by the great variability of the variables, or may be an error due to a mistake which can be treated as a missing data however the mistake should be clarified.

Sensitivity Analysis: Sensitivity analyses are a series of analyses conducted against the unexpected conditions, e.g. analysis for data with missing data filled in, subgroup analysis, analysis for a different dataset, adjustment of different covariates, etc. The sensitivity analysis result will be compared with that from the due analysis to explore the robustness of inferences. Sensitivity analysis results can be a supportive data to the main analysis, however, it cannot be the primary rational to make a conclusion.

The sensitivity analysis method is the same as the pharmacokinetic similarity method.

Sensitivity analysis on the outlier or other cases can be conducted, if warranted, during the PK similarity analysis. Influence of outliers can be evaluated by comparing the assessment results in cases with the outliers excluded or not. Reasons should be explained if different conclusions are reached.

5.5 Immunogenicity Assessments

For population included in Immunogenicity Analysis Set (IAS), data will be summarized and listed by treatment, by visit, and by treatment and visit.

Incidence and severity of immunogenicity response (ADA/Nab).

5.6 Safety Analysis

5.6.1 Adverse Event

Adverse Event (AE) – Any untoward medical occurrence in a clinical investigation participant administered a pharmaceutical product and that does not necessarily have a causal relationship with this treatment. An AE can therefore be any unfavorable and unintended sign (including an abnormal laboratory finding), symptom, or disease temporally associated with the use of a medicinal (investigational) product, whether or not related to the medicinal (investigational) product.

Serious Adverse Event (SAE) – Any untoward medical occurrence that at any dose:

- Results in death,
- Is life-threatening,
- Requires inpatient hospitalization or prolongation of existing hospitalization,
- Results in persistent or significant disability/incapacity, or
- Is a congenital anomaly/birth defect.

Suspected Unexpected Serious Adverse Reaction (SUSAR) – an adverse reaction that meets three criteria: suspected, unexpected and serious.

- Suspected: There is a reasonable possibility that the drug caused the adverse drug reaction.
- Unexpected: An adverse reaction, the nature or severity of which is not consistent with the applicable product information (e.g., the reference safety information).
- Serious: See above for SAE.

Severity:

Intensity to be graded refer to CTCAE (Common Terminology Criteria for Adverse Events) 5.0 as:

DEGREE	DESCRIPTION
Grade 1	Mild, asymptomatic or mild symptoms; clinical or diagnostic observations only; intervention not indicated.
Grade 2	Moderate, minimal, local or noninvasive intervention indicated; limiting age-appropriate instrumental activities of daily living (ADL). Instrumental ADL refer to preparing meals, shopping for groceries or clothes, using the telephone, managing money, etc.
Grade 3	Severe or medically significant but not immediately life-threatening; hospitalization or prolongation of hospitalization indicated; disabling; limiting selfcare ADL. Selfcare ADL refer to bathing, dressing and undressing, feeding self, using the toilet, taking medications, and not bedridden.
Grade 4	Life-threatening consequences; urgent intervention indicated.
Grade 5	Death related to AE.

Relationship to investigational products, to be classified into as: Related; Probably related; Possibly related; Unlikely; Unrelated. AEs related, probably related and possibly related to investigational products are considered to be drug related adverse reactions.

Related	
 With plausible time relationship Consistent with the known mechanism of action, properties or adverse reactions A positive dechallenge observation A positive rechallenge observation Cannot be explained from other plausible aspects
Probably related	
 With plausible time relationship Consistent with the known mechanism of action, properties or adverse reactions A positive dechallenge observation Lack of evidence of a positive rechallenge observation Cannot be explained from other plausible aspects
Possibly related	
 With plausible time relationship Lack of evidence of a positive rechallenge observation Any condition in which: 
 1) Consistent with the known mechanism of action, properties or adverse reactions; A positive dechallenge observation; Can be explained from other plausible aspects 2) Consistent with the known mechanism of action, properties or adverse reactions; Lack of evidence of a positive dechallenge observation; Cannot be explained from other plausible aspects 3) Inconsistent with the known mechanism of action, properties or adverse reactions; A positive dechallenge observation; Cannot be explained from other plausible aspects 4) Inconsistent with the known mechanism of action, properties or adverse reactions; Lack of evidence of a positive dechallenge observation; Cannot be explained from other plausible aspects
Unlikely	
 With an improbable time relationship (but not impossible) Lack of evidence of a positive dechallenge observation Lack of evidence of a positive rechallenge observation Any condition in which: 
 1) Consistent with the known mechanism of action, properties or adverse reactions; Can be explained from other more plausible aspects 2) Inconsistent with the known mechanism of action, properties or

	adverse reactions; Can be explained from other plausible aspects
Unrelated	
Without plausible time relationshipInconsistent with the known mechanism of action, properties or adverse reactionsLack of evidence of a positive dechallenge observationLack of evidence of a positive rechallenge observationCan be explained from other plausible aspects

Adverse events leading to withdrawal: Adverse events that selected "Yes" to "Discontinued due to Adverse Event?".

Adverse events leading to death: Adverse events of " Death related to AE / Grade 5 " intensity.

5.6.2 Laboratory Examination

Laboratory tests include biochemistry, hematology and urinalysis. Descriptive statistics is used to describe the results of biochemistry, hematology and the changes of biochemistry and hematology results from pre-dose to post-dose. The N, mean, standard deviation, median, quartile, minimum and maximum of the results will be calculated, changes from pre-dose to post-dose will be described.

The shift table is used to describe the changes of clinical evaluation before and after taking medication, and the N and percentage of participants' test results will be calculated.

List the participants with clinical significance after taking medication.

The results of laboratory tests will be tabulated.

5.6.3 Physical Examination

The shift table is used to describe the changes of the results before and after taking medication, and the N and percentage of the results of the physical examination items will be calculated.

The results of the physical examination of the participants will be tabulated.

5.6.4 Vital Signs

Descriptive statistics is used to describe each item of the participants' vital signs and the changes from pre-dose to each time point after taking medication and N, mean, standard deviation, median, quartile, minimum and maximum will be calculated.

The shift table is used to describe the changes in clinical evaluation from pre-dose to post-dose. N and percentage of the results of each test item will be calculated.

The results of the vital signs of the participants will be tabulated.

5.6.5 ECG

The shift table is used to describe the changes of ECG examination from pre-dose to post-dose, and the N and percentage of participants for ECG results will be calculated.

The results of ECG items will be tabulated.

